#### **9.4.1.7 Sequential Organ Failure Assessment Score**

Sequential Organ Failure Assessment score (SOFA) and its change from baseline will be summarized by treatment group per infection site at Baseline, EOT, TOC, and FU. Change from baseline will also be summarized. In addition, SOFA score regardless of primary infection diagnosis will be analyzed in a similar manner.

#### **9.4.1.8 Clinical Pulmonary Infection Score**

For the HABP/VABP/HCABP subjects, CPIS at EOT, TOC, and FU will be summarized by treatment group.

#### **9.4.1.9 Composite of Survival and No Change in Antibiotic Treatment**

For the composite of survival and no change in antibiotic treatment due to either lack of therapeutic benefit or drug-related toxicity at TOC, the response rate with 95% CI by treatment group per infection site will be presented. This composite endpoint will be assessed by Shionogi medical expertise internally. The response rate in the cefiderocol treatment group will be compared with that in the BAT group using Cochran Mantel-Haenszel Method stratified by infection site. The 95% CI will be calculated by Wald method (see [Appendix 2](#)).

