### 4.2 Randomization to Treatment Groups

The treatments will be randomized to subject identification numbers by the IXRS® provider in a 2:1 fashion, i.e., 2  $\times$  cefiderocol and 1  $\times$  BAT. An interactive web or voice response system (IWRS/IVRS) will be used to assign subjects to identification numbers for which treatment has already been randomly assigned. Randomization will be performed by the stochastic minimization method using their infection site (HABP/VABP/HCABP, cUTI, and BSI/sepsis), APACHE II score ( $\leq$  15 and  $\geq$  16), and region (North America, South America, Europe, and Asia-Pacific) as allocation factors. To avoid deterministic allocation based on the ongoing allocation results, probabilistic allocation will be incorporated.

The population with HABP/VABP/HCABP will be approximately 50% of randomized subjects; cUTI is limited to no more than 30% of randomized subjects, and the remainder of subjects will be enrolled under the BSI/sepsis diagnosis. The randomization ratio of subjects between treatment groups based on clinical diagnosis will be maintained through the allocation factor of clinical diagnosis at the time of randomization. The process for

---

subject number assignment and treatment assignment is described in the study procedure manual.

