### 6.2 Statistical Testing

No inferential testing will be performed except for the exploratory analysis described in Section 9.4.1.7. If statistical tests are performed, they will be performed at the 0.05 significance level using 2-sided tests, except where otherwise noted. No multiplicity adjustment of statistical tests will be applied in this study.

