## Appendix 2 Calculation Confidence Interval for Cochran-Mantel-Haenzel Test

Let  $x_{ij}$  and  $n_{ij}$  denote the number of responders and the total number of patients in treatment  $i$  and stratum  $j$ , respectively, where  $i=1,2$  represents the treatment group (cefiderocol or BAT) and  $j = 1,2,3$  represents the stratum, the following  $2 \times 2$  contingency table shows the total number of subjects and the number of responders in each treatment arm at stratum  $j$ .

Category	cefiderocol	BAT
Response	$x_{1j}$	$x_{2j}$
No Response	$n_{1j} - x_{1j}$	$n_{2j} - x_{2j}$
Total	$n_{1j}$	$n_{2j}$

The proportion of patients with response ( $\pi_{ij}$ ) in treatment  $i$  and stratum  $j$  can be estimated by:

$$\hat{\pi}_{ij} = x_{ij}/n_{ij}$$

and the stratum-specific proportion difference ( $d_j$ ) is estimated by:

$$\hat{d}_j = \hat{\pi}_{1j} - \hat{\pi}_{2j}.$$

The adjusted estimate of the difference in the rate of responders between the two treatment groups ( $d_{adj}$ ) is given as:

$$\hat{d}_{adj} = \sum_{j=1}^3 w_j \hat{d}_j$$

using the CMH weights defined as  $w_j = \left( \frac{n_{1j}n_{2j}}{n_{1j}+n_{2j}} \right) / \sum_{j=1}^3 \frac{n_{1j}n_{2j}}{n_{1j}+n_{2j}}$ .

Hence, the 2-sided stratified 95% Wald-type confidence intervals of  $d_{adj}$  based on the CMH weights is constructed as:

$$\hat{d}_{adj} \pm z_{\alpha/2} \text{Var}(\hat{d}_{adj}),$$

where the variance of  $d_{adj}$  is given as:

$$\text{Var}(\hat{d}_{adj}) = \sqrt{\sum_{j=1}^3 \hat{w}_j^2 \left( \frac{\hat{\pi}_{1j}(1 - \hat{\pi}_{1j})}{n_{1j}} + \frac{\hat{\pi}_{2j}(1 - \hat{\pi}_{2j})}{n_{2j}} \right)},$$

and  $z_{\alpha/2}$  is the 97.5th percentile of the standard normal distribution.

[REDACTED] [REDACTED]  
Reason for signing: Approved

[REDACTED]  
Date of signature: 27-Jun-2019 17:37:01 GMT+0000

Reason for signing: Approved

[REDACTED]  
Date of signature: 27-Jun-2019 18:12:40 GMT+0000

Signature Page for [REDACTED]

[REDACTED]

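### The SAP's only between-arm test omits APACHE II, an allocation factor; adjusting for it costs little and gains power only if APACHE II predicts the composite

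*SAP*

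**What the plan says.** Allocation (SAP 4.2; also Protocol 5.4): "Randomization will be performed by the stochastic minimization method using their infection site (HABP/VABP/HCABP, cUTI, and BSI/sepsis), APACHE II score" in two levels (≤15, ≥16), "and region (North America, South America, Europe, and Asia-Pacific) as allocation factors".

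Comparison (SAP 9.4.1.9): the cefiderocol response rate on the composite "will be compared with that in the BAT group using Cochran Mantel-Haenszel Method stratified by infection site", with a 95% Wald interval. Appendix 2 builds "The adjusted estimate of the difference in the rate of responders between the two treatment groups" from three strata, the infection sites. SAP 9.4.1 places the analysis in the CR Micro-ITT population.

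Status (SAP 6.2): "No inferential testing will be performed except for the exploratory analysis described in Section 9.4.1.7". Section 9.4.1.7 is the SOFA section, which contains only summaries; the comparison sits in 9.4.1.9. If tests are run, "they will be performed at the 0.05 significance level using 2-sided tests", and "No multiplicity adjustment of statistical tests will be applied in this study".

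APACHE II elsewhere: Protocol 7.4.2 describes it as a measure of severity. SAP 6.1 says the corrected score is used in analysis. SAP 9.3.3 plans APACHE II subgroups for clinical outcome, microbiological outcome and Day 28 mortality, but not for this composite. Protocol 9.9.4 plans the comparison by infection site. Neither document gives response rates by APACHE II level, an effect size or a power for the composite.

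**The concern.** Minimization makes the arms alike on APACHE II. If APACHE II also predicts the response, the treatment difference then varies less from trial to trial than a test that ignores APACHE II assumes. The CMH p-value is too large on average: its true level falls below 5% and some power is lost. In a trial of about 150 patients with one inferential comparison, it is wasteful to leave out a variable that is already collected, already used for allocation and already defined for analysis.

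The interval raises a separate question. In Appendix 2 an arm-by-site cell with 0% or 100% response contributes no variance at all, and two of the three BAT strata are small. The interval can therefore be too narrow while the p-value beside it is too large.

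**Working it through.** **The plan's own figure.** 150 × 2/3 = 100 on cefiderocol, as SAP 4.3 states, which leaves 50 on BAT. With the site mix in SAP 4.2 (about 50% pneumonia, at most 30% cUTI, the remaining 20% BSI/sepsis), BAT has about 25, 15 and 10 patients per site. If 120 of the 150 are analysed, these become 20, 12 and 8. The size of CR Micro-ITT is not given.

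**Assumptions, because the documents give no rates.** Overall response 0.60; APACHE II split 50/50; gap g between APACHE II groups from 0 to 40 points; treatment effect 0 or +22 points; minimization probability 0.90 when cefiderocol is favoured and 0.80 when BAT is; region mix 15/10/45/30% with no effect on response; membership of the analysis set random with respect to arm.

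**Large-sample size of the site-only test.** With APACHE II balanced but left out, the share of outcome variance it explains is f = (g/2)² / (0.60 × 0.40), and the true level is 2 × [1 − Φ(1.96/√(1 − f))]. At g = 0.30, f = 0.0225/0.24 = 0.094 and the level is 0.0395.

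**Simulation.** 20,000 trials per setting, all 150 analysed, CMH without continuity correction. Simulation error is about 0.0015 on size and 0.3 points on power.

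| Gap (points) | Formula size, site only | Simulated size, site only → six strata | Power, site only → six strata | Appendix 2 Wald non-coverage, three strata |
|---|---|---|---|---|
| 0 | 0.0500 | 0.051 → 0.052 | 74.0% → 73.4% | 0.059–0.061 |
| 10 | 0.0488 | 0.049 → 0.050 | 74.3% → 73.9% | 0.059 |
| 20 | 0.0453 | 0.045 → 0.048 | 74.6% → 75.5% | 0.053–0.055 |
| 30 | 0.0395 | 0.038 → 0.047 | 75.6% → 78.3% | 0.046–0.049 |
| 40 | 0.0318 | 0.031 → 0.049 | 76.4% → 81.9% | 0.039–0.042 |

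The change in power from adjusting is −0.6, −0.4, +0.9, +2.7 and +5.5 points.

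**Is the balancing the cause?** When allocation balances site only, at a 30-point gap, the site-only test keeps its level (0.048). The conservatism therefore comes from minimizing on APACHE II and then ignoring it.

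**Smaller analysis sets.**
- 75% of the 150 analysed: power moves 61.3% → 60.4% with no gap, 62.0% → 65.2% at 30 points (+3.2) and 62.2% → 69.0% at 40 points (+6.8). Size at 30 points moves 0.042 → 0.049.
- A separate simulation, 80% analysed and a 20-point effect: power moves 55.4% → 54.8%, 57.1% → 60.5% and 57.8% → 64.6% at gaps of 0, 30 and 40 points. Size moves 5.0% → 4.8%, 4.4% → 5.2% and 4.1% → 5.1%.

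**The interval.** Each arm-by-site variance term in Appendix 2 is p(1 − p)/n, which is zero at p = 0 or 1.
- Three strata: with 75% analysed, non-coverage is 0.062, 0.058, 0.055 and 0.047 at gaps of 0, 20, 30 and 40 points. A separate check with fixed stratum sizes and response rates of 60% to 95% gives coverage of 93.1% to 93.8% (40/24/16 versus 20/12/8) and 93.6% to 94.0% (50/30/20 versus 25/15/10).
- Six strata, same Wald formula: non-coverage is 0.066–0.069 with all 150 analysed and 0.073–0.075 with 75%. Coverage is about 92.5% to 93.4%.
- Six strata, Sato variance: it rejects 5.5% to 6.2% under the null, so coverage is 93.8% to 94.5%, better but not exact.

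**Region.** Adding it gives 3 × 2 × 4 = 24 strata, or 50/24 ≈ 2 BAT patients per stratum even if all 150 are analysed.

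**The case against.** The best defence is that little depends on this test. The SAP labels it exploratory, the endpoint is secondary, the primary analyses are descriptive rates with intervals, no power is claimed, and a conservative p-value does not create false positives. Stratifying by site also follows Protocol 9.9.4. All of this stands and limits the weight of the point.

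A second defence is that APACHE II may predict this composite only weakly. The composite is not mortality alone: it also counts antibiotic changes for lack of benefit or toxicity, and it includes cUTI. Scores above 30 are excluded (Protocol 4.3), and ventilated, sedated patients may be given a Glasgow Coma Scale of 15 (Protocol 7.4.1). This also stands, so the size of the gain has to be stated conditionally.

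A third is that the remedy is incomplete. It still omits region, and the corrected APACHE II score may differ from the one used for allocation. It also thins small strata: on a 50/50 split of 120 analysed patients, the cUTI and BSI/sepsis BAT strata of 12 and 8 become about 6 and 4 per cell. These are fair costs, but with no APACHE II gap the simulated loss of power is only about 1 point at most.

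A reader might infer three stronger things that the documents do not support:
- That APACHE II is the main prognostic factor, so that the test certainly runs below 5%. Nothing in the documents says so or quantifies it.
- That the comparison as a whole is conservative. For small to moderate gaps the Wald interval errs the other way.
- That restricting to CR Micro-ITT creates an APACHE II imbalance that biases the result. Carbapenem resistance is judged on baseline specimens, and the simulations removed patients at random, so such an imbalance is neither documented nor tested here. Conservatism also depends on balance: at a 30-point gap, size moves back from 0.038 to 0.042 when only 75% are analysed.

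**Conclusion.** The omission is real and unexplained, and its effect is conditional. If APACHE II predicts the composite, the site-only CMH p-value is conservative. The cost is negligible for gaps up to about 20 points, about 3 points of power at 30 and 5 to 7 at 40; with no gap, nothing meaningful is lost by adjusting. The three-stratum Wald interval is a separate, small defect: about 93% to 95% coverage for small to moderate gaps, and worse if carried over to six strata. These sizes rest on the assumed response rates, APACHE II split and minimization probabilities above. The wrong section number in SAP 6.2 needs no assumption: read literally, the SAP does not authorise the one test it plans. This is a free or cheap improvement to an exploratory analysis and does not touch the primary results.

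**What to change.** - SAP 9.4.1.9: stratify the CMH test and the adjusted difference by infection site × APACHE II (≤15, ≥16; corrected score as in SAP 6.1), six strata, with zero weight for any stratum in which one arm is empty. Keep the site-only result as supplementary.
- Appendix 2: let the stratum index run from 1 to 6 and replace the Wald variance with the Mantel-Haenszel (Sato) variance or a stratified score interval. Say that Sato coverage is about 94% to 94.5%, not exact. Do not carry the present Wald formula over to six strata.
- State that region is left out because the cells would be too sparse.
- SAP 6.2: change the reference from 9.4.1.7 to 9.4.1.9.

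The cost is SAP wording and a few lines of code, with no new data. The downside is sparser strata.

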## **10. SAFETY**

Safety assessments included adverse events (AEs), clinical laboratory safety tests (hematology, chemistry, and specialized test), vital sign measurements. All safety summaries and analyses will be performed based on the Safety population.

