**Table 7-1 Clinical Laboratory Tests**

Category	Evaluation Items
Hematology Tests	Hematocrit, Hemoglobin, Platelet count, RBC count, WBC count with differential and morphology indices INR and PTT
Blood Chemistry Tests	ALP, ALT, AST, GGT, LDH, CPK, CRP, and Amylase BUN, Creatinine, TBL Sodium (Na), Potassium (K), Bicarbonate (HCO 3 ), Chloride (Cl), Calcium (Ca), Magnesium (Mg) Glucose, Total protein, Albumin, Uric acid, Total cholesterol
Urinalysis	Glucose, Blood, Protein, Ketones, Bilirubin, Urobilinogen, Leukocyte esterase, Microscopic a (WBC, RBC, Crystal and casts)
Specialized Tests	Iron, TIBC, Transferrin iron saturation, and Hepcidin at Screening and TOC
Others	Serum or urine pregnancy: at Screening CrCl and eGFR at Screening and EA CrCl determined from a timed urine collection at EA b

RBC = red blood cell; WBC = white blood cell; INR = international normalized ratio; PTT = partial thromboplastin time; ALP = alkaline phosphatase; ALT = alanine aminotransferase; AST = aspartate aminotransferase; GGT = gamma glutamyl transferase; LDH = lactate dehydrogenase; CPK = creatine phosphokinase; CRP = C-reactive protein; BUN = blood urea nitrogen; TBL = total bilirubin; TIBC = total iron-binding capacity; TOC = test of cure; CrCl = creatinine clearance; eGFR = estimated glomerular filtration rate; EA = early assessment

a If sediment is present

b For patient with eGFR  $\geq$  90 mL/min/1.73 m^2 at Screening

Blood and urine samples for clinical laboratory tests will be collected at specified times. Blood samples for all clinical laboratory tests will be collected in the fasted state, if possible.

The samples other than some specialized tests will be measured at a local laboratory and results will be entered in the eCRF. The samples for serum iron, TIBC, transferrin iron saturation, and hepcidin will be shipped to a central laboratory. Details procedures for sample collection, handling, labeling, storage, and shipping will be provided in the separate study procedure manual. Shipping labels, instructions for shipping and courier service will be provided from the sponsor or CRO.

The investigator or sub-investigator will assess whether any abnormal changes from baseline are clinically significant (See also Section 7.12.6).

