False positive urinalysis tests for protein or ketones (by dipstick) were found in the previous Phase 1 study (Study R2111). In the case that a positive dipstick test is found, the result will be confirmed by a secondary laboratory method.

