#### **9.10 Safety Analyses**

Safety assessments include AEs, mortality for up to EOS, clinical laboratory tests (hematology, chemistry, and urinalysis), and vital signs. Safety analyses will be performed for the safety population.

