### **9.10.3 Clinical Laboratory Analysis**

Summary statistics for laboratory test data will be presented for each scheduled timepoint and for the change from baseline to each timepoint. Baseline will be the last value obtained before randomization.

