## 10.2 Clinical Laboratory Evaluations

Summary statistics for laboratory test data (hematology and serum chemistry parameters, and other specialized tests) will be presented for each scheduled time point measured

after randomization and for the change from baseline to each time point. If a site reports a laboratory value including sign for numeric value (i.e. “<”, “>”), the value removing sign will be used for analysis.

The number and percentage of subjects with the following prespecified outlier category (Table 10-1) during the postdosing period including unscheduled will be presented by treatment group.

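### Urinalysis is part of the protocol's safety analysis, but the SAP's laboratory summaries omit it, and the SAP neither lists nor justifies the departure

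*SAP*

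**What the plan says.** Protocol 9.10 sets the scope of the safety analysis: "Safety assessments include AEs, mortality for up to EOS, clinical laboratory tests (hematology, chemistry, and urinalysis), and vital signs". Protocol 9.10.3 then says what is done with the laboratory part and excludes no category: "Summary statistics for laboratory test data will be presented for each scheduled timepoint and for the change from baseline to each timepoint". The synopsis (Safety Assessments) and Appendix 1 schedule urinalysis at Screening, EA, EOT, TOC and FUP. Day 14 is added if treatment is extended, and EOS if an abnormal result needs follow-up.

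SAP 10 gives a different list: "Safety assessments included adverse events (AEs), clinical laboratory safety tests (hematology, chemistry, and specialized test), vital sign measurements". SAP 10.2 repeats that scope for the summaries: "Summary statistics for laboratory test data (hematology and serum chemistry parameters, and other specialized tests) will be presented". Table 10-1, the by-arm outlier table, has no urine parameter. Protocol Table 7-1 defines the specialized tests as "Iron, TIBC, Transferrin iron saturation, and Hepcidin at Screening and TOC".

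Protocol 9.1 requires departures from the protocol's analyses to be described and justified in the SAP. SAP 15, the list of changes from the protocol, has no entry on urinalysis, and neither does the SAP revision record.

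**The concern.** A safety summary that the protocol promises would not be produced, and nothing in the SAP tells a reader that it was removed or why. Assessing the safety of S-649266 is a named secondary objective, and renal safety is a reasonable interest in this trial. BAT may be polymyxin-based. Appendix 3 of the protocol urges caution when colistimethate is combined with other potentially nephrotoxic drugs. Protocol 5.3 has renal function checked at EA for changes due to treatment.

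There is also a drug-specific reason to handle urine results by a stated rule. The note after Protocol Table 7-1 reports false-positive dipstick protein and ketones in Phase 1 and requires a second method to confirm a positive. Without a planned summary, neither the initial nor the confirmed results are tabulated by arm, so a real urine finding and a dipstick artefact cannot be told apart at group level.

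**Working it through.** No sample size, power or event figure is involved. The check is a comparison of the texts.

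| Item | Protocol | SAP |
|---|---|---|
| Laboratory categories in the safety analysis | Hematology, chemistry, urinalysis (9.10) | Hematology, chemistry, specialized tests (10) |
| Categories given summary statistics | All laboratory test data (9.10.3) | Hematology, serum chemistry, specialized tests (10.2) |
| Urine parameters in the outlier table | No such table | 0 of 12 parameter entries (Table 10-1) |
| Departure recorded | Required (9.1) | 0 entries in SAP 15 or the revision record |

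**Could *specialized tests* include urine?** No. Table 7-1 lists urinalysis and specialized tests as separate categories, and the second holds only iron studies and hepcidin.

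**Is it a slip in one sentence?** Unlikely. SAP 10 and SAP 10.2 carry the same list, and Table 10-1 agrees with both.

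**Does the SAP normally disclose such removals?** Yes. SAP 10.2 excludes PTT and gives the reason, that it was reported mixed with APTT. The revision record logs both that exclusion and the deletion of the ECG section. SAP 15 records changes as small as the reference point for prior and concomitant medication.

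**Where do urine results go under the SAP as written?** There are two routes.

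1. *Listings.* SAP 10.2 lists all local and central laboratory data, but promises out-of-range flags for central measurements only. Under Protocol 7.7.2.1 only the specialized tests go to the central laboratory, so urinalysis is local. Urine results are therefore listed with no flag promised.
2. *Adverse events.* Protocol 7.12.6 has laboratory results that the investigator considers clinically significant, urinalysis included, recorded as AEs. SAP 10.1 summarises AEs by arm. If the abnormality belongs to a disease or organ toxicity, only that diagnosis is reported. The judgement is made in an open-label study (Protocol 5.5).

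What remains without a by-arm summary is therefore every urine result that was not judged clinically significant.

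**What renal information remains by arm?** SAP 10.2 summarises serum chemistry. Table 10-1 adds outlier counts for serum creatinine (rise of at least 0.3 mg/dL) and BUN (rise of at least 50% to above the upper limit of normal). These do not show protein or blood in urine.

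**The case against.** The strongest reply is that little is lost. Clinically significant urine findings reach the by-arm AE tables, creatinine and BUN are summarised by arm, and every result is listed. This stands, and it limits the point: it would be wrong to say that proteinuria and hematuria go unreported by arm. It does not remove the point. The AE route depends on an unblinded judgement, a table of recorded results does not, and the protocol promised the latter.

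A second reply is that the data are hard to interpret. Patients with cUTI, up to 30% of those randomized, must have pyuria at entry and may have catheters, obstruction or intrinsic renal disease. The dipstick has known false positives. Results come from local laboratories at about 100 sites, and the SAP analyses only local data that convert to standard units. All of this is fair. It argues for a simple, well-labelled table, or for a stated reason to list only. It does not argue for silent omission.

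Third, neither document promises a shift table, and change from baseline does not suit dipstick grades. This is also fair. Protocol 9.1 summarises categorical variables by counts and percentages, which would meet the commitment.

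Fourth, the table shells are a separate document (SAP 1) and are not available here. A urinalysis table there cannot be excluded, but the SAP text does not provide for one.

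A reader might also infer that renal toxicity is an expected difference between the arms. The documents do not say so. Protocol 9.13 lists renal toxicity monitoring as a resource-use item, Appendix 3 concerns combining nephrotoxic drugs, and excretion of about 90% of S-649266 unchanged in urine is a pharmacokinetic fact.

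**Conclusion.** The point holds as an undisclosed departure from the protocol's safety analysis. One of the three laboratory categories named in Protocol 9.10 has no planned summary in the SAP, and the justification that Protocol 9.1 requires is missing. The practical loss is confined to urine results that did not become AEs. No primary or secondary efficacy result is affected.

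Two further readings on size go too far. Five routine visits in about 150 patients give 5 × 150 = 750 scheduled urinalyses, which a reader might take as a minimum. For those five visits it is a ceiling: it assumes that every patient survives and attends to FUP, in a trial with mortality endpoints at Day 14 and Day 28, and 150 of the 750 are Screening samples. Day 14 or EOS samples would be extra in some patients. Likewise, casts are not collected from every patient at every visit, because Table 7-1 makes microscopy conditional on sediment.

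The conclusion assumes that the SAP text governs what is produced and that the unseen shells add no urinalysis table.

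**What to change.** Restore urinalysis in SAP 10 and SAP 10.2 and add one categorical table by treatment group. Either counts and percentages by visit or a shift from baseline (as defined in SAP 6.5) to the worst post-baseline result would do. Cover protein, blood and ketones, plus microscopy with the number of patients in whom sediment was examined as denominator.

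Two rules should be written in:

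- For a positive protein or ketone dipstick, use the confirmatory result where it was captured. The protocol requires confirmation but does not say that the result has its own eCRF field, so check this before the rule is fixed. If it was not captured, label the table as unconfirmed dipstick results.
- Show cUTI patients separately for blood and white cells, since their infection alone can produce these findings.

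If the sponsor prefers listing only, SAP 15 should say so and give the reason, as SAP 10.2 does for PTT.

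The cost is SAP wording and one extra table from local results that Protocol 7.7.2.1 already sends to the eCRF, with some work to align grading between laboratories. The downside is that the data are semi-quantitative and of limited interpretability, which a footnote should state. Patient care and data collection do not change.
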